5.0 Data management

5.1 Data storage

Any data collected on paper will be stored in a designated locked cabinet at the research site. Data will be entered into an OMR sheet for accuracy. All electronic data collected will be kept in a password secured portable computer and backed up to dedicated password protected local back-up drive every week.

Some measures may include password protection, security under lock and key, access controlled office, etc. To protect patient confidentiality, records and logs will be stored in locked file cabinets, in locked offices, and on computers protected by a password. A patient identification log will also be put in place - each patient's data will be coded with an identifier, and the key to the code will be located in another physical location or on a separate computer. All patient identification logs will be kept for 6 years, after which it will be securely disposed of. The data will only be accessible to the study team members involved in and approved for the study. Identifiers of participants (i.e. birth certificate numbers, date of birth, email addresses, mailing addresses) will be extracted and each patient will be allocated an individual number to secure patient's identity. All data will be kept for 6 years upon completion of study.

5.2 Data Safety Monitoring

Data safety monitoring will be performed by the investigator and a team of co-investigators. Data at each site will be reviewed on a weekly basis by the PI. Data on adverse events/ serious adverse events will be monitored for safety of participants and reported accordingly.

Any data and safety information will be communicated to research members by the PI both verbally and by email circulation, and will be documented accordingly. The PIs will be responsible for doing Monthly or Adhoc meeting to discuss and update data and safety information with study team.

The PI or Co-Is will be responsible for verifying that the information entered into the data collection sheet is in accordance to what is in the clinical notes. Periodic monitoring of the study data collected will be monitored by a designated personnel who will be assigned to audit the study. This person will be trained by NUHS Research Office to conduct monitoring of clinical trial data recorded, and also compliance to SGGCP, SOPs and trial protocols and other regulations.

6.0 Potential difficulties and limitations

6.1. Issues with Recruitment

Recruitment of sufficient participants to reach adequate power for the study may be a challenge. We hope that a multi-centre approach will help increase the caption group and thus increase patient numbers. Furthermore, publicity will be carried out to heighten the awareness of the trial among dentists, and to increase the number of children recruited for the clinical trial. Advertisement emails through the Singapore Dental Association, dental specialist societies, and Oral and Maxillofacial staff at NUH will be distributed. A poster for recruitment of participants will be put up in designated rooms and waiting areas for each of the research sites. A copy of the Poster and Letter to the Singapore Dental Association for recruitment of participants are as in **Appendix H1 & H2**.

6.2. Ensuring patient return for reviews

As this is a randomized controlled clinical study, it is possible that patients may not return for recalls following completion of procedures, resulting in drop outs. As such, a 10% margin for drop outs has been assumed in the power calculation. Intention to treat analysis will also be carried out.

Patients enrolled in the study will be followed up closely, and appointments at appropriate intervals as specified in the protocol will be made. Patients will be reminded to attend the review visits 2 days in advance via telephone or SMS. Treatment rendered and review visits will not be charged.

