3.4.2.3 Review visits and parameters for evaluation of clinical outcomes

The primary purpose of review appointments is to assess healing and continued root development. Patients will be reviewed according to the set protocol stated above. Each tooth will be accounted for as an individual case, regardless of whether it originates from the same patient or not. Data will be recorded into a data collection sheet (**Appendix F**) and transferred into an Excel spreadsheet prior to analysis.

During the review visits, the following outcomes will be assessed:

Clinical-

- Presence/absence of tooth
- Mobility
- Periodontal probing (6 point evaluation for pocket depth)
- Tenderness to percussion and palpation
- Percussion note
- Free from pain or discomfort
- No evidence of labial swelling or abscess, signifying continued presence of infection
- Presence of discolouration

Radiographic

Standardised periapical radiographs will be taken before the start of treatment, at the end of the treatment and then again at each recall visit post treatment. Final outcome measures will be recorded at the 18th month review. This protocol is a standard clinical protocol and no additional radiographs will be taken for the purposes of this study.

A standardized beam aligning holder for both direct and indirect sensors will be utilized during taking of radiographs. All radiographs will be evaluated for periapical status and qualitative and quantitative status of root dimensions.

Standard Pulp Sensibility Tests

At each recall, pulp sensibility responses will be evaluated using thermal test (EndoIce) and Electric Pulp Test (EPT). Evaluation of tooth mobility, tenderness to percussion and palpation will also be carried out. This procedure will be done at the baseline, and during each subsequent review visit following completion of treatment.

Photography

Standardized intra-oral photographs will be taken before the start of the treatment and each recall visit. Post treatment crown colour in comparison to the pre-operative photographs and to that of the contralateral tooth will be assessed using the MathWorks software as described in the study by Day et al

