3.5 Sample size calculation

This sample size is likely to be achievable given the expected number of cases that will be available in the clinics employed in this proposal. Retrospective data available from the School Dental Service, Health Promotion Board showed that RET treatment was provided to 78 patients (with 85 teeth) over a period of 3 years 6 months (Mar 2009 to Dec 2012). 77.2% of these teeth were mandibular premolars, 13.9% were maxillary incisors, and 8.9 % were maxillary premolars. Of these, 69.4% (n=59) had successful outcomes with closed apices following RET treatment, 7.1% (n=6) showed signs of increased root length and dentine wall thickening but were still undergoing review, 5.9% (n=5) did not show signs of root growth but demonstrated resolution of periapical pathology, 8.2% (n =7) had unfavourable outcomes with apices remaining open and signs of periapical pathology, and 9.4% (n=8) were loss to follow up.

The proposal will be for a sample size of 30 teeth per group, i.e. total estimated recruitment is 60 teeth. The sample size proposed is calculated based on data obtained from a published paper by Bose et al (2009). The sample size is estimated based on changes in root length as the primary outcome measure. Using a 2-sided sample test, assuming a mean difference between the groups of 1.5 and SD of 2, (at a significance level of 0.05 and 80% power), the sample size required is 30 subjects per group, i.e. 60 subjects in total. It is our hope that a multi-centre approach will help increase the caption group and thus increase patient numbers.

This is in agreement with sample size proposed in existing on-going randomized control trials which are registered on the Clinical Trial database website: www.clinicaltrials.gov. The clinical trials have similar age-range of potential patients as the proposed study.

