4.5. Statistical methods

All analysis will be carried at a tooth level, where each tooth will be accounted for as an individual case. Descriptive statistics (both discrete and non-discrete variables), which will include means, standard deviations, frequencies and percentages will be determined. Data will be checked for homogeneity of variance prior to application of statistical tests. Appropriate correlation and regression analysis will be

employed in consultation with a biostatistician. Inter and intra-operator variability scores will be evaluated using Kappa statistics. The significance level will be set at $p<0.05$. All data will be analyzed using SPSS Statistical Package (IBM SPSS Statistics).

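### Section 6.2 claims a 10% drop-out margin, but 30 per group leaves only about 3–7%, and power after 10% loss is about 77–79%, not 80%

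*Protocol*

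**What the plan says.** Protocol section 3.5 names the outcome that sizes the trial: "The sample size is estimated based on changes in root length as the primary outcome measure". The inputs follow, "assuming a mean difference between the groups of 1.5 and SD of 2, (at a significance level of 0.05 and 80% power"), with a two-sided test, and the result is that "the sample size required is 30 subjects per group, i.e. 60 subjects in total". The same section sets recruitment at the same figure, this time counted in teeth: "The proposal will be for a sample size of 30 teeth per group, i.e. total estimated recruitment is 60 teeth". It does not mention drop-out in the calculation, and no larger recruitment figure appears elsewhere in the protocol.

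Section 6.2, on keeping patients in follow-up, then states that "a 10% margin for drop outs has been assumed in the power calculation".

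Two further statements bear on this. Section 3.5 reports of the earlier service series of 85 teeth that "9.4% (n=8) were loss to follow up". On the unit of analysis, section 3.4.2.3 says "Each tooth will be accounted for as an individual case" and section 4.5 says "All analysis will be carried at a tooth level".

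**The concern.** If a 10% allowance were built in, the number recruited would exceed the number that must be evaluable by a factor of 1/0.9. In section 3.5 the required number and the recruited number are the same, and both are close to what the stated inputs give with no allowance at all. Section 6.2 therefore appears to claim protection that the calculation does not contain.

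The consequence is that readers are told 80% power for root length survives 10% attrition when it is only partly protected. The point is not hypothetical: the protocol's own earlier series lost 9.4%, and section 6.1 already says that recruiting enough participants for adequate power may be difficult.

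A smaller matter in the same paragraph is that the 30 is given once as teeth and once as subjects. These are different counts (the earlier series had 85 teeth in 78 patients), and the analysis is by tooth.

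**Working it through.** **Inputs.** From section 3.5: difference 1.5, SD 2, two-sided α = 0.05, power 80%. From section 3.1: 1:1 allocation. From section 6.2: loss 10%. Standardised difference d = 1.5/2 = 0.75. Teeth are treated as independent, as the protocol's own calculation does.

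**Step 1: the plan's own figure.**

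- Normal approximation: n = 2(z₀.₉₇₅ + z₀.₈₀)²/d² = 2(1.960 + 0.842)²/0.75² = 27.9, so 28 per group.
- Two-sample t test (noncentral t): n = 28.9, so 29 per group.

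The stated 30 is thus reproduced to within one or two per group with no drop-out allowance.

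**Step 2: the margin that 30 contains.**

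- t test: (30 − 29)/30 = 3.3%.
- Normal approximation: (30 − 28)/30 = 6.7%.

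**Step 3: power by evaluable number per group.** The normal-approximation column is Φ(d√(n/2) − 1.960); the other is from the noncentral t.

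| Evaluable per group | t test | Normal approximation |
|---|---|---|
| 30 (no loss) | 81.5% | 82.8% |
| 29 | 80.1% | 81.5% |
| 28 | 78.7% | 80.1% |
| 27 (10% loss) | 77.2% | 78.7% |

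Ten per cent of 30 is 3, leaving 27. The earlier series' loss, 8/85 = 9.4%, leads to the same place: 30 × 0.906 = 27.2, so 27. The shortfall against 80% is 2.8 points (t test) or 1.3 points (normal approximation).

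**Step 4: what a 10% margin would correspond to.**

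- t test: 29/0.9 = 32.2, so 33 per group (66 in total).
- Normal approximation: 28/0.9 = 31.1, so 32 per group (64 in total).
- The laxer rule of adding 10% gives 29 × 1.1 = 31.9, so 32, or 28 × 1.1 = 30.8, so 31.

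**Step 5: could 30 already include the margin?** One-sided testing needs 22 (normal) or 23 (t test) per group, and 25 or 26 after inflation. That is not 30, and the protocol specifies two-sided testing. The division 27/0.9 = 30 is exact, but 27 arises only by rounding 27.9 down, and 27 per group misses 80% under both methods (step 3).

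**The case against.** The best defence is that this is a gap of rounding size rather than a missing allowance. The bare inputs give 28 or 29, not 30, so something was added; truncating 27.9 to 27 and dividing by 0.9 gives exactly 30, which may be how the figure arose. The larger shortfall of 2.8 points assumes a t test, which the protocol does not name. Planning uncertainty is also bigger than the gap: at 27 per group an SD of about 1.97 (normal) or 1.93 (t test) would restore 80%, while an SD of 2.1 would put power at about 78% (t test) even with all 30. Finally, complete-case power is a worst case. Radiographs are taken at six recalls, intention-to-treat analysis is announced, and section 6.2 provides reminders and free reviews.

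Much of this stands as a limit on importance. Part of the allowance is there, the shortfall is small, and earlier radiographs could recover some of it. It does not rescue the sentence. The truncation route starts from 27 per group, which is already underpowered by either method. A different SD is not the one the protocol assumed. Announcing intention-to-treat does not by itself supply the missing 18-month root lengths. How those are handled may be settled in the statistical analysis plan, but that plan cannot make section 6.2 a true description of section 3.5.

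It is also fair to say that the teeth-or-subjects wording does not affect the drop-out arithmetic; it is a tidying point within the same paragraph. Likewise, all the power figures, including those proposed below, hold only if teeth from the same patient are independent, and the corrected text should say so.

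**Conclusion.** The concern holds. On the protocol's own inputs, 30 per group carries a margin of 3.3% (t test) or 6.7% (normal approximation), not 10%. With 10% lost, power for root length is 77.2% or 78.7%, so the statement in section 6.2 is wrong as written. The effect is modest: 1.3 to 2.8 points of power, or 2 to 3 teeth per group. It should be corrected, but it does not threaten the trial.

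The figures rest on equal loss in the two groups, no outcome information from lost teeth, an SD of 2, and independence of teeth.

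**What to change.** In section 3.5, count in teeth only and add text such as:

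> Twenty-nine evaluable teeth per group give 80% power (two-sample t test, treating teeth as independent). With 30 teeth enrolled per group and 10% loss, 27 per group are evaluable and power is about 77% (complete cases).

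In section 6.2, replace the sentence on the 10% margin with:

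> A loss of about 10% is expected. The 30 per group is not fully inflated for it; the resulting power is given in section 3.5.

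This needs no extra patients and no change to the analysis. The only cost is a slightly less favourable stated power. If the sponsor would rather make the 10% claim true, 33 teeth per group would correspond to 80% power after that loss (t test), at a cost of 6 more teeth in total; the wording change does not require this.

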6.3. Technical difficulties with radiographic analysis

With respect to radiographic analysis, there is a possibility of radiographic distortion and differences in angulations between pre and post-operative radiographs. We sought to minimize these errors by using a cone aligning holder. All available radiographs will be evaluated at the same time, and using the same computer under standardized lighting conditions. Calibration of radiographs using the computerized program VixWin and Image J (used to evaluate radiographic measurements) will be done prior to data analysis. The scale will be set for the digital films on the basis of the pixel size used in the VixWin digital system.

7.0 Timeline

- Start date: When DSRB and HSA CTC approval is obtained
- End date: (Proposed) Data collection to end by two years after last subject enrolled; closure by two and half years after last subject enrolled.

The study will be conducted according to all the principles of International Conference of Harmonisation-Good Clinical Practice (ICH-GCP) as well as the Singapore Guideline for Good Clinical Practice (SGGCP). The trial will be subjected to the regulations as stated in the Medicines Act and Medicine (Clinical Trials) Regulations. The trial will be registered with the appropriate institution review boards, as well as clinical trial databases both internationally (e.g. www.ClinicTrials.gov) and locally.

8.0 Impact of the study and Future directions

Traditional endodontic treatment in immature teeth do not have a good outcome as it has been shown that the failure rate of teeth treated using such approaches is very high (1). The use of RET has the potential to revolutionize the management of non-vital teeth with incomplete root development. Continued root development and thickening of the dentine walls of the root canals through regeneration method would mean that such teeth may survive for the lifetime of the patients.

An important aspect is that we will test the significance of the use of antibiotics. So far no study of this design has been conceived. Should the results of this study demonstrate that antibiotics are not required for achieving success in RET procedures, the need for antibiotics and hence risk of adverse drug reactions and emergence of resistance strains will be reduced. The streamlining of disinfection protocols for RET procedures will also make it easier for dental practitioners to perform this treatment for their patients.

Alongside the study on long-term outcomes and success rates of the two different protocols, this project will also study the patient reported outcomes (PRO), which is necessary to evaluate the young patient's perspective on treatment rendered, and has yet to be studied and reported in current literature. Results of the study will be presented at international conferences and published in relevant scientific journals. Given that only a few groups worldwide are working on this subject, such data generated from our study will contribute to knowledge on this subject globally and secure NUS/HPB an international impact in this field of clinical research.

References

1. Cvek M. Prognosis of luxated non-vital maxillary incisors treated with calcium hydroxide and filled with gutta-percha. A retrospective clinical study. *Endod Dent Traumatol* 1992;8(2):45-55.
